**Secondary Outcomes (Patient-Centered Outcomes):**

- Health status at 30 days, 3 months, and 6 months as measured by the EuroQol-5D-5L
- Time from injury to return to work or usual activity (days)
- Time from injury to resolution of pain (days)

**STUDY POPULATION**

All adult trauma patients admitted with a blunt chest injury to Memorial Hermann – TMC Emergency Department (ED) will be screened for this trial. Patient meeting the eligibility criteria listed below will be approached for participation in this trial.

**Inclusion Criteria:**

- Age  $\geq 16$  years\*\*
- Blunt trauma mechanism
- Severe chest wall injury:
  - Radiographic flail segment (defined as  $\geq 2$  fractures in  $\geq 3$  consecutive ribs) -or-
  - $\geq 5$  consecutive rib fractures -or-
  - $\geq 1$  rib fractures with bicortical displacement
- At least one true rib (1-7) fractured and accessible for stabilization

\*\*Subjects sixteen years of age and older are considered as adult trauma subjects in a large percent of the trauma centers. Sixteen and seventeen year olds are able to drive in most states and are at high risk for motor vehicle accidents resulting in blunt or penetrating injuries. Excluding this age group would significantly decrease the external validity of the proposed project. Additionally, it is difficult to differentiate a 16 or 17 year old from one who is 21 or older at the time care is initiated in the ED until positive identification can be obtained. Children 15 years of age or younger or less than 50 kg body weight will be excluded from this trial. Children's intravascular volume is different than the adult's, requiring adjustments to the standard adult treatment protocols.

**Exclusion Criteria:**

- Age  $< 16$  years
- Severe traumatic brain injury (best resuscitated GCS  $\leq 8$  as measured at 24h)
- Spinal cord injury
- Pre-existing congestive heart failure or oxygen-dependent pulmonary disease
- Any reason for which SSRF could not occur within 72 hours of admission

## STUDY PROCEDURES

### Screening:

Clinical research staff are available 24/7 to conduct screening upon ED admission. The research staff will continue to monitor those patients who have experienced blunt chest trauma with possible rib fractures. Patients and/or their legally authorized representative (LAR)/family member that are eligible for the study will be approached for participation in the trial. An informed consent will be obtained prior to randomization.

### Randomization:

Eligible subjects who have consented to participate will be randomized into one of two groups: 1) Control arm or 2) Intervention arm. The two arms are described in detail below. A 1:1 allocation ratio using a permuted block design of 4 or 6 will be used to ensure equal number of patients in each group. Randomization will be performed using the randomization module in REDCap and stratified by unit of admission.

Control Arm: Control patients will receive usual care per our established institutional guidelines, consisting of pulmonary toilet, lung volume expansion exercises, and a multimodal approach to oral pain medication management. For severe pain not responding to oral therapy, intravenous narcotics, lidocaine, or ketamine may be added. Regional analgesia techniques such as epidural analgesia, paravertebral analgesia, and intercostal nerve blockade may also be considered. The pain medication regimen is deescalated as pulmonary status and pain control allow.

(<https://med.uth.edu/surgery/files/2017/06/Chest-Management-of-Multiple-Rib-Fractures-2013.pdf>)

For patients who fail all of these therapies and desire to proceed with SSRF, the procedure may be offered late, as salvage therapy.

Intervention Arm: The intervention will consist of early surgical stabilization of the fractured ribs plus usual care. If randomized to SSRF, the procedure should occur as early as possible (given the patient clinical status and need for more emergent procedures), ideally within the first 72 hours of hospital admission. Since stabilization of all fractures may not be possible due to anatomic exposure (e.g., the first, second, and third ribs may be difficult to access due to their location), the surgery must stabilize at least one true rib (ribs 1-7). Stabilization of the true ribs is considered more critical due to their greater contribution to chest wall volume and mechanical respiratory function.

Observation Arm: Patients refusing consent to randomization will be invited to participate in the observational arm. Patients selecting this option will be asked to complete the same assessments as the randomized groups.

Equipment: In order to maintain a pragmatic approach, surgical stabilization will be performed using any commercially available internal rib fixation system, at the discretion of the operating surgeon.

### Data Collection

The clinical research staff will follow the subjects throughout their hospitalization (or up to 30 days, whichever comes first) for complications such as surgical site infections, pneumonia, need for reoperative procedures and other complications commonly associated with rib fractures.

The data will be reviewed and entered into the UT Redcap database. Each subject will be assigned a study specific number. The subject's medical record and the MHH-TMC trauma registry will be utilized for data collection purposes. Data will be collected until discharge or 30 days (whichever occurs first) and questionnaires will be conducted up to 6 months post ED admission.

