### Secondary Outcomes (Clinical Metrics):

- Mortality
- Incidence of respiratory failure requiring mechanical ventilation > 24 hours
- Incidence of tracheostomy
- Inpatient incidence of pneumonia
  - >10,000 cfu/mL on bronchioalveolar lavage -or-
  - Clinical diagnosis of pneumonia with subsequent antibiotic treatment
- Utilization of regional anesthesia (binary outcome)
- Opioid usage (continuous and binary)
- Lengths of stay
  - Hospital-free days (= 30 minus number of hospital days; in-hospital death = 0)
  - Ventilator-free days (= 30 minus number of ventilator days; in-hospital death = 0)

- ICU-free days (= 30 minus number of intensive care unit days; in-hospital death = 0)
- Re-intervention rates for surgical complications, including bleeding, seroma, and surgical site infection

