### Follow Up

Subjects will be asked to complete a health status questionnaire at 30 days, 3 and 6 months post ED admission. The EuroQol-5D-5L form will be utilized to complete the questionnaire. This questionnaire will be completed in person (if subject is scheduled for a routine clinic visit at those timepoints) or via telephone conversation. The purpose of this questionnaire is to collect information pertaining to the patient-centered outcomes. A member of the research team will conduct the follow up questionnaires for the outcomes.

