### **DATA AND SAFETY MONITORING**

An internal data and safety monitoring board (DSMB) will review the study at 50% enrollment to evaluate for substantial benefit or harm to one of the treatment groups. The DSMB committee will consist of an independent surgeon, statistician, and clinician to be named that is not affiliated with the clinical care of the patient population. The DSMB will review the information collected to address the primary and secondary outcomes. The DSMB will provide a report following their review after 75 subjects have been enrolled which will include a decision on how trial enrollment shall proceed.

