#### Anxiety)

- I am not anxious or depressed
- I am slightly anxious or depressed
- I am moderately anxious or depressed
- I am severely anxious or depressed
- I am extremely anxious or depressed

“Your Health Today” (0-100)

Are you back to work or usual physical activity? (yes/no)

If yes, when?

Has your rib pain completely or almost completely resolved? (yes/no)

If yes, when?

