#### Appendix B. List of Data Elements to be Collected

Study number

Gender (male/female)

Age

Race (white, black, Hispanic, Asian, other, unknown)

Trauma type (blunt/penetrating)

Mechanism (MVC, MCC, fall, auto pedestrian, ATV, assault, crush, GSW, stab, other)

Date/time of injury

PH vital signs

Transfer? (yes/no)

ED arrival date/time

ED vitals

ED CBC

ED BMP

ED rTEG

ED lactate

ED base excess

Unit of admission

Randomization group (SSRF/usual care)

R 1st rib fx?

Segmental?

Displaced?

R 2nd rib fx?

Segmental?

Displaced?

R 3rd rib fx?

Segmental?

Displaced?

R 4th rib fx?

Segmental?

Displaced?

R 5th rib fx?

Segmental?

Displaced?

R 6th rib fx?

Segmental?

Displaced?

R 7th rib fx?

Segmental?

Displaced?

L 1st rib fx?

Segmental?

Displaced?

L 2nd rib fx?

Segmental?

Displaced?

L 3rd rib fx?

Segmental?

Displaced?

L 4th rib fx?

Segmental?

Displaced?

L 5th rib fx?

Segmental?

Displaced?

L 6th rib fx?

Segmental?

Displaced?

L 7th rib fx?

Segmental?

Displaced?

Radiographic flail segment? (yes/no)

Flail chest? (yes/no)

Right clavicle fx? (yes/no)

Left clavicle fx? (yes/no)

Right scapula fx? (yes/no)

Left scapula fx? (yes/no)

Mechanical ventilation immediately prior to SSRF? (yes/no)

Tracheostomy prior to SSRF? (yes/no)

Clinical suspicion of PNA prior to SSRF? (yes/no)

Chest tube prior to SSRF? (yes/no)

Date/time of SSRF

Time from admission to SSRF (hours)

Procedure time (min)

Hardware system (Synthes/KLS Martin)

Right ribs stabilized by SSRF

1 (yes/no)

2 (yes/no)

3 (yes/no)

...

Left ribs stabilized by SSRF

1 (yes/no)

2 (yes/no)

3 (yes/no)

...

VATS? (yes/no)

Thoracotomy? (yes/no)

w-RTS

ISS

AIS head/neck

AIS face

AIS chest

AIS abdomen

AIS extremity

AIS external

Regional analgesia for rib fxs? (yes/no)

If yes, what kind? (epidural, paravertebral, intercostal, serratus plane, other)

Post-SSRF PNA? (yes/no)

Post-SSRF hardware infection? (yes/no)

Post-SSRF seroma requiring intervention? (yes/no)

Post-SSRF hematoma requiring intervention? (yes/no)

Post-SSRF hardware failure? (yes/no)

Post-SSRF need for hardware removal for any reason? (yes/no)

Post-SSRF SSI? (yes/no)

Superficial? (yes/no)

Deep? (yes/no)

Organ space? (yes/no)

DVT? (yes/no)

PE? (yes/no)

Discharge date/time

Discharge disposition (home, rehab, SNF, LTAC, transfer to other hospital, level 1 psych, morgue, other)

Total opioid use (MME)

MME/day

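### No capture of surgical complications is planned after discharge, so the re-intervention outcome is an in-hospital rate whose window shrinks as SSRF shortens the stay

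*Combined protocol and SAP*

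**What the plan says.** The Data Collection section says that research staff "will follow the subjects throughout their hospitalization (or up to 30 days, whichever comes first) for complications such as surgical site infections", pneumonia, reoperation and other complications. It then repeats the limit for the data as a whole: "Data will be collected until discharge or 30 days (whichever occurs first) and questionnaires will be conducted up to 6 months post ED admission".

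The clinical secondary outcomes include "Re-intervention rates for surgical complications, including bleeding, seroma, and surgical site infection". No time window is attached, whereas the pneumonia outcome in the same list is expressly limited to inpatient events. Appendix B adds postoperative items on hardware infection, seroma, hematoma, hardware failure and surgical site infection, and "Post-SSRF need for hardware removal for any reason? (yes/no". These are yes/no items without an event date.

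Of the calls or visits after discharge, the Follow Up section says: "The purpose of this questionnaire is to collect information pertaining to the patient-centered outcomes". The form in Appendix A holds the EQ-5D-5L, a 0-100 health score, return to work or usual activity, and rib pain. Appendix B adds survival, ability to answer and consent to be asked at 1, 3 and 6 months. Neither appendix has a readmission item.

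**The concern.** Re-intervention is the one listed outcome specific to complications of the tested operation, and it is observed only while the patient is in hospital. A patient discharged on day 6 who returns with a wound infection or a hardware problem has no planned way of being counted.

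Hospital stay is also the primary outcome. The more SSRF shortens the stay, the less time remains in which its complications can be recorded, so a favourable primary result and a low complication rate are linked by the way data are collected. The DSMB, which is to "evaluate for substantial benefit or harm to one of the treatment groups", reviews the information collected for these same outcomes and would see the same in-hospital counts.

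**Working it through.** The documents give no complication rate, onset time or postoperative window, so there is no stated figure to reproduce. What can be computed is how long operated patients are observed.

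**Inputs**
- Control stay: median 10 days, IQR 6-15 (Sample Size Calculation).
- SSRF stay: median 7 days if the planned effect occurs (same section); 10 days if SSRF does not change stay.
- Time to surgery, d: 0 to 3 days, from the aim of operating within 72 hours (Study Design; Randomization).
- Assumption: stay is log-normal, with the control arm's log-scale spread in both scenarios.

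**Spread.** Log SD = ln(15/6) / (2 × 0.6745) = 0.916 / 1.349 = 0.679. With a median of 10, this gives quartiles of 6.3 and 15.8 days, close to the stated 6 and 15.

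**Postoperative window** = min(stay, 30) − d.

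*Simple subtraction at the median.* For a stay of 7: 7 − 0 = 7 days to 7 − 3 = 4 days. For a stay of 10: 10 − 0 = 10 days to 10 − 3 = 7 days.

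*Share observed for 14 days or more, median stay m:* 1 − Φ(ln((14 + d)/m) / 0.679). For m = 7 this is 13.1% (d = 1), 11.2% (d = 2) and 9.6% (d = 3).

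*Excluding stays that end before the day of surgery*, since those patients could not have been operated on that day. For m = 7 and d = 3, 89.4% of stays exceed 3 days, so the share is 0.096 / 0.894 = 10.7%. Simulating all combinations this way gives:

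| Median stay | Surgery day | Median window (days) | Observed ≥14 days |
|---|---|---|---|
| 7 | 0 | 7.0 | 15.4% |
| 7 | 1 | 6.0 | 13.2% |
| 7 | 2 | 5.2 | 11.5% |
| 7 | 3 | 4.7 | 10.7% |
| 10 | 0 | 10.0 | 30.9% |
| 10 | 1 | 9.0 | 27.6% |
| 10 | 2 | 8.1 | 24.7% |
| 10 | 3 | 7.3 | 22.5% |

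**Which limit binds.** About 2% of stays reach 30 days at a median of 7 and about 5% at a median of 10. For nearly everyone the stop is discharge, not day 30.

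**Coverage of the first 30 postoperative days.** On average 21-29% is observed at a median stay of 7, and 31-40% at 10.

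**Link to the primary outcome.** With surgery on day 1, moving the median stay from 10 to 7 days cuts the median window from 9.0 to 6.0 days and the share observed for 14 days or more from 27.6% to 13.2%.

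**The case against.** Several points on the other side are fair.

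- *The amount missed is unknown.* A reader might infer that surgical harm is undercounted by a definite amount. The documents give neither event rates nor onset times, so they support only this: later events have no planned route into the data. This stands.
- *A window of a few days is one scenario.* The 7-day stay is the effect the trial hopes to show. At a median of 10 days the window is longer, and even at 7 days a quarter of patients are observed beyond about 9 to 11 days. This stands, which is why both stays are shown.
- *Re-intervention is not the only harm measure.* A reader might take it as the trial's main harm outcome. The plan does not rank it so. It also lists mortality, respiratory failure, tracheostomy and pneumonia, follows survival to 6 months, and collects health status, rib pain and return to activity after discharge. Lasting effects of a late complication could show there, though not as counted events.
- *Staff might still record a late event.* The medical record and trauma registry are named sources, the trial is single-centre, and the Appendix B items carry no time limit. But Data Collection ends collection at discharge or day 30 and no later review is planned. Incidental capture would leave a rate with no defined period at risk.
- *The window is disclosed.* A careful report could label the rate as in-hospital. The outcome definition itself does not.

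**Conclusion.** The point holds as a gap in outcome definition and data capture. The plan names re-intervention for surgical complications without a window, stops looking at discharge for nearly all patients, and has no later contact or record review that would find such events. Median postoperative observation is about 4 to 7 days at a median stay of 7 and about 7 to 10 days at a median stay of 10, with about 10-15% and 22-31% observed for 14 days or more.

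These figures rest on the planning stays, the log-normal assumption with a common log SD of 0.68, and surgery on day 0 to 3. The 72-hour target is worded as an ideal, and controls may have late salvage SSRF; surgery later in a given stay leaves a shorter window.

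The result would be an in-hospital rate that risks understating surgical harm, by an amount that cannot be computed from the documents. The analysis of hospital stay is not affected.

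**What to change.** 1. In Data Collection and the secondary outcome list, define surgical-complication outcomes over 30 days from the date of surgery, the same for every operated patient whatever the stay, including controls who have salvage SSRF. Report events up to the 6-month contact as a second, longer-term rate.
2. Add dated yes/no items to the existing 30-day, 3-month and 6-month form: readmission, treated wound infection, chest-wall reoperation and hardware removal.
3. Use the medical record, already a named source, to complete the 30-day window. The contacts are timed from ED admission, so after surgery on day 3 the 30-day call covers only 30 − 3 = 27 postoperative days.
4. Give the DSMB the 30-day rates available at its review. If 150 patients accrue evenly over 18 months, the review at 75 falls near month 9, when only those enrolled in the first 3 months (about 25) would have 6-month data. The 30-day rate is therefore the more useful one at that point.

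The cost is a short protocol and database change, a few more questions at contacts already scheduled, and some record checks. Some events treated elsewhere will rest on patient report, and the reported complication rate is likely to look less favourable.

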### Follow Up

Subjects will be asked to complete a health status questionnaire at 30 days, 3 and 6 months post ED admission. The EuroQol-5D-5L form will be utilized to complete the questionnaire. This questionnaire will be completed in person (if subject is scheduled for a routine clinic visit at those timepoints) or via telephone conversation. The purpose of this questionnaire is to collect information pertaining to the patient-centered outcomes. A member of the research team will conduct the follow up questionnaires for the outcomes.

### **DATA AND SAFETY MONITORING**

An internal data and safety monitoring board (DSMB) will review the study at 50% enrollment to evaluate for substantial benefit or harm to one of the treatment groups. The DSMB committee will consist of an independent surgeon, statistician, and clinician to be named that is not affiliated with the clinical care of the patient population. The DSMB will review the information collected to address the primary and secondary outcomes. The DSMB will provide a report following their review after 75 subjects have been enrolled which will include a decision on how trial enrollment shall proceed.

### **STATISTICS**

The primary and secondary outcomes will be analyzed on an intention to treat basis, though a per protocol analysis will also be performed. Demographics, injury characteristics, and eligible rib fracture patterns will be reported. Subgroup analyses will be stratified *a priori* by unit of admission. All statistical analyses will be performed using STATA® (version 15.1; StataCorp; College Station, TX) and R© (The R Foundation) commercially available software.

### Sample Size Calculation

We expect to enroll 150-250 total patients. We calculated the effect size we will be able to detect in hospital LOS, assuming a median LOS of 10 days (IQR 6-15) in the control group and two-sided alpha of 0.05. A sample size of 150 patients (75 per group) will provide 85% power to detect a difference of 3 days (*i.e.*, median LOS of 7 days in intervention group). With a sample size of 250 patients, we will have 89% power to detect a difference of 2.5 days in hospital LOS.

### Frequentist Analysis

Generalized linear models (GLMs) will be used to analyze all outcomes and will include treatment group and unit of admission (stratifying variable) as covariates. For LOS outcomes, negative binomial or zero-inflated negative binomial (for outcomes with large number of zeros; *e.g.*, ventilator days, ICU days) regression models will be used. Binary outcomes will be analyzed with log binomial regression models to estimate relative risks (RRs). For longitudinal outcomes, we will use mixed models including treatment group, time, and center as covariates and a random intercept (and slope if needed) for subject. We will report RRs or group differences and 95% confidence intervals for all outcomes.

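### Time to return to work and time to pain resolution have no model or rule for patients without an event date by 6 months, and an ordinary GLM on days would analyse only those who recovered

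*Combined protocol and SAP*

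**What the plan says.** The patient-centred secondary outcomes include "Time from injury to return to work or usual activity (days") and "Time from injury to resolution of pain (days"). Both appear in the Hypothesis section, where surgery is expected to shorten them. Return to work or usual activity is also part of Aim 3.

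The analysis text is general: "Generalized linear models (GLMs) will be used to analyze all outcomes", with treatment group and unit of admission as covariates. Specific models follow for three outcome types only:
- length of stay: negative binomial, zero-inflated where needed
- binary outcomes: log binomial
- longitudinal outcomes: mixed models

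On effect measures it says: "We will report RRs or group differences and 95% confidence intervals for all outcomes". The Bayesian Analysis section carries the same models over. The Statistics section adds: "The primary and secondary outcomes will be analyzed on an intention to treat basis".

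The data come from two questions at the end of the Appendix A questionnaire: "Are you back to work or usual physical activity? (yes/no") and "Has your rib pain completely or almost completely resolved? (yes/no"). Each asks for the date only after a yes. Under Data Collection, "questionnaires will be conducted up to 6 months post ED admission".

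The Limitations section describes how contact will be kept, cites 95% follow-up at 6 months in another trial at the institute, and says that dropouts will be examined if loss is large. A rule for death is given only for hospital-, ventilator- and ICU-free days.

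**The concern.** A time in days exists only for a patient who has had the event and reported it. A patient reached at 6 months who is still off work or in pain has been fully followed but has no value for the outcome. The same holds for a patient who dies or is lost first. The two outcomes fit none of the three named model types, so they fall under the general GLM sentence without a family, a censoring rule or an assigned value.

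The plan does not say that these patients will be left out. But a GLM fitted to days in its ordinary form needs a number for each patient, so it would leave them out. The arms would then be compared among recovered patients only, and recovery is a post-randomisation event that the treatment is meant to change. If surgery brings more patients to recovery by 6 months, the control arm loses more of its slowest patients, and the apparent benefit shrinks. These are stated hypotheses of the trial, so a diluted estimate and lost power matter.

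**Working it through.** **Plan's own figures.** None concerns these outcomes; the Sample Size Calculation covers hospital stay only. That calculation is not in dispute. A negative binomial Wald test (mean 11.4 and dispersion 0.40, fitted to median 10 and IQR 6-15) gives 86.6% and 89.4%, against the stated 85% and 89%.

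**Inputs.**
- Follow-up T = 182 days (6 months).
- 75 per arm, or 125 per arm if 250 are enrolled (Sample Size Calculation).
- 70 days of lost work or activity (Background Information). The text does not say whether this is a mean or a median, so both readings are used for the control arm. It is a background figure, not a planning value.
- Assumed: exponential times, proportional hazards, no deaths, recovery hazard ratio (HR) 1.3 or 1.5 for surgery.

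**Formulas**, for event rate r:
- without a date at T: u = exp(-rT)
- restricted mean: RM = (1 - u)/r
- mean among patients with a date: E = (RM - T·u)/(1 - u)

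The control rate is 1/70 (mean 70) or ln 2/70 (median 70). The surgical rate is HR times that.

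**Difference in recovery, HR 1.3, no loss.**

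| Control reading | No date, control vs surgery | E (days) | Ratio of E | RM (days) | Ratio of RM |
|---|---|---|---|---|---|
| Mean 70 | 7% vs 3% (about 6 vs 3 of 75) | 55.4 vs 47.4 | 0.86 | 64.8 vs 52.0 | 0.80 |
| Median 70 | 17% vs 10% (about 12 vs 7 of 75) | 65.0 vs 58.3 | 0.90 | 84.3 vs 70.2 | 0.83 |

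The difference in days is 8.0 instead of 12.8 on the first reading, and 6.7 instead of 14.1 on the second.

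**Adding loss.** Independent exponential loss of proportion p by T has rate l = -ln(1 - p)/T. Observed event times then have rate k = r + l, truncated at T, and the proportion with a date is (r/k)(1 - exp(-kT)).
- HR 1.3, 5% loss in both arms: no date in 9% vs 5%, then 18% vs 11%. The ratio among dated patients stays at 0.86, then 0.90.
- HR 1.0, equal loss: ratio 1.00.
- HR 1.0, 5% loss in one arm and 15% or 20% in the other: means of 54.8 vs 53.6 or 53.0 days (mean 70), and 64.4 vs 63.0 or 62.2 days (median 70). The ratio is 0.98 or 0.97, so the arm with more loss looks slightly faster.

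**Power**, two-sided 5%, no loss, 10,000 simulated trials per case. Each cell gives the Wald test on the log mean ratio among dated patients, then the log-rank test on all patients.

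| HR | Per arm | Mean 70 | Median 70 |
|---|---|---|---|
| 1.3 | 75 | 20% vs 35% | 13% vs 33% |
| 1.3 | 125 | 29% vs 52% | 19% vs 49% |
| 1.5 | 75 | 43% vs 67% | 26% vs 64% |
| 1.5 | 125 | 63% vs 87% | 40% vs 86% |

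At HR 1.0 both tests rejected in 4.8% to 5.5% of trials.

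**Slower recovery**, HR 1.5, 75 per arm, gamma log-link GLM on dated patients against log-rank (1,500 trials per case):
- Control median 120 days: 34.9% vs 20.7% without a date, ratio among dated patients 0.90, power 11% vs 55%.
- Control median 180 days: 49.6% vs 34.9% without a date, ratio 0.94, power 8% vs 45%.

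**The case against.** The strongest reply is that this is an omission plus a hypothetical. The plan never says that patients without a date are dropped, and some GLMs can handle censoring, such as a Poisson model with an exposure offset. That is true. But no such form is named, and the general sentence with its listed effect measures is all an analyst would have.

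Second, the yes/no answers at 1, 3 and 6 months could be analysed by log binomial or mixed models, which would keep unrecovered patients. That would be a sound analysis of a different outcome: the plan defines both outcomes in days.

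Third, the sizes rest on a borrowed 70 days that concerns work and activity. Nothing in the documents gives a time for pain resolution. This stands. The figures illustrate the mechanism and do not bound it, and slower recovery makes the shrinkage worse.

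Fourth, the loss model records events continuously, whereas dates are obtained at three contacts. A patient who recovers and is then lost before the next contact also has no date. With contacts at 30, 91 and 182 days and 20% loss, the share without a date rises from about 13% to 17% (mean 70) and from 23% to 26% (median 70). The ratios barely move.

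Fifth, log-rank is favoured under proportional hazards. A restricted-mean comparison at HR 1.3 with 75 per arm has 30% to 33% power, still well above 20% or 13%.

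The high follow-up cited in Limitations does not answer the point. It concerns loss, and a patient who is reached and answers no is not lost.

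**Conclusion.** The concern holds and should be fixed. The plan assigns a model class to two time-to-event outcomes without saying how patients with no event date enter it. In its ordinary form that model excludes them, which conflicts with the intention-to-treat basis.

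The main consequence is a diluted effect and lost power, not a false positive. Under the assumptions above, a 17% to 20% reduction in restricted mean time appears as 10% to 14%, and power at HR 1.3 falls by roughly two-fifths or more. With identical recovery and equal loss and death there is no bias. Unequal loss of the size tested moves the ratio by only 2% to 3%.

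The omission itself is certain from the text. The sizes depend on assumed exponential recovery, proportional hazards, no deaths and the 70-day figure. The primary outcome and the sample size are unaffected.

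**What to change.** State in the SAP that these two outcomes are exempt from the general GLM sentence. Analyse them as times to event up to 6 months, adjusted for unit of admission, in both the frequentist and the Bayesian analyses. Any of these would do:
1. A difference in 6-month restricted mean time, with death counted as not recovered.
2. A cause-specific Cox model, with cumulative incidence curves and death as a competing event.
3. A named censoring-capable GLM.

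Censor lost patients at the last completed questionnaire. The choice among the three is a matter of preference. The necessary part is a method that handles censoring, plus a written rule for unrecovered, dead and lost patients.

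The cost is a few sentences, slightly more analysis work, and a hazard ratio in place of an RR if Cox is chosen. There is one small data point. Appendix A already asks for event dates, but Appendix B lists survival at 1, 3 and 6 months only as yes/no, with no date of death and no questionnaire date. In-hospital deaths can be dated from discharge time and disposition, except possibly those after day 30, when hospital data collection stops. Either add the two date fields or state that nominal 1-, 3- and 6-month times are used. Option 1 needs no date of death.
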